#### *Missing Data*

Because the snapshot algorithm is a single imputation method that includes a “No virologic data” category (i.e., data can still be missing), we will use multiple imputation that assumes missing at random as a sensitivity analysis. We will create 100 imputed data sets using appropriate FCS model and combine results using Rubin’s rules. We will also present estimates assuming “best case” (i.e., probability of event = 0) and “worst case” (i.e., probability of event = 1) scenarios, as a sensitivity analysis. Of note, we will impute whether the participant was < or  $\geq$  the cut-off value (50 or 200), not the plasma RNA HIV-1 value, for missing study visits prior to implementing the snapshot algorithm.

#### Supplementary Analyses

Supplementary analyses for the secondary virologic outcome measures will include all participants (Cohort 1-naïve and Cohort 1 rollovers) who received study products. All intercurrent

events and missing data will be handled as described in the snapshot algorithm. The sensitivity analyses described above will be implemented.

## 7 Report Contents

This section lists the major report contents that may be included the Primary Analysis Reports. Detailed descriptions of the content of each of the following sections are given in the AIP.

- 1** Introduction
- 2** Background
  - I. Study Design
  - II. Objectives
  - III. Outcome Measures
  - IV. Study History and Monitoring History
- 3** Statistical Considerations
  - I. Analysis Populations
  - II. General Considerations
  - III. Estimands and Estimation
- 4** Disposition
  - I. CONSORT Diagram
  - II. Screening
  - III. Accrual
  - IV. Protocol Deviations
  - V. Evaluability
- 5** Baseline Characteristics
- 6** Study Status and Retention
- 7** Status of Drugs under Study
- 8** Primary Analyses
- 9** Secondary Analyses
- 10** Other Analyses
- 11** Summary

**8     Associated Documents**

**Attachment 1: Writing Team Roster**

**Attachment 2: Snapshot Algorithm (using cut-off of HIV-1 RNA 200 copies/mL)**

Condition (‘Week 24’ indicates Week 24 window/‘Week 20’ indicates Week 20 window)	Response	Reasons
1. If non-permitted change in background therapy prior to Week 24/Week 20	HIV1-RNA $\geq$ 200	Change in ART
2. If permitted change in background therapy prior to Week 24/Week 20 AND the latest on-treatment VL prior to/on the date of change is $\geq$ 200 copies/mL	HIV1-RNA $\geq$ 200	Change in ART
3. If non-permitted change in background therapy during Week 24/Week 20 
 
Last on-treatment VL during Week 24/Week 20 prior to/on the date of change <math>\geq</math> 200 copies/mL
 
Last on-treatment VL during Week 24/Week 20 prior to/on the date of change <200 copies/mL
 
No VL during Week 24/Week 20 prior to/on the date of change
 
	HIV1-RNA $\geq$ 200 HIV1-RNA < 200 HIV1-RNA $\geq$ 200	Data in window and HIV-1 RNA $\geq$ 200 copies/mL  Change in ART
4. If permitted change in background therapy during Week 24/Week 20 AND the last on-treatment VL prior to/on the date of change is $\geq$ 200 copies/mL 
 
This last on-treatment VL occurs prior to Week 24/Week 20
 
This last on-treatment VL occurs during Week 24/Week 20 but prior to/on the date of change
 
	HIV1-RNA $\geq$ 200 HIV1-RNA $\geq$ 200	Change in ART Data in window and HIV-1 RNA $\geq$ 200 copies/mL
5. If none of the above conditions met 
 
VL available during Week 24/Week 20                             
 
Last on-treatment VL during Week 24/Week 20 <math>\geq</math> 200 copies/mL
 
Last on-treatment VL during Week 24/Week 20 < 200 copies/mL
 
 
 
No VL during Week 24                             
 
If subjects still on study (i.e. IP has not been permanently stopped up to Week 24)
 
If subjects withdraw before/during Week 24 due to
 
 
 
	HIV1-RNA $\geq$ 200 HIV1-RNA < 200 No virologic data at Week 24 Window	Data in window and HIV-1 RNA $\geq$ 200 copies/mL  On study but missing data in window



- Safety reasons (e.g. AE/death, liver chemistry stopping criteria, renal toxicity withdrawal criteria, QTc withdrawal criteria et al, as recorded in eCRF Conclusion form)

- Non-safety related reasons (e.g. Lack of efficacy, protocol deviation, withdrew consent, loss to follow-up, study closed/terminated, investigator discretion et al, as recorded in eCRF Conclusion Form)

	No virologic data at Week 24 Window	Disc due to AE/death

o Last on-treatment VL <200 c/mL OR no on-treatment VL available during study

	No virologic Data at Week 24 Window	Disc for other reasons

o Last on-treatment VL <math>\geq</math> 200 c/mL AND withdrawal due to Lack of efficacy

	HIV1-RNA $\geq$ 200	Disc. for lack of efficacy

o Last on-treatment VL <math>\geq</math> 200 c/mL AND withdrawal due to all other non-safety related reasons

	HIV1-RNA $\geq$ 200	Dis. for other reason and HIV-1 RNA $\geq$ 200 copies/mL

Note the same process will be mapped out for Week 48.

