Participants who prematurely discontinue injectable study product permanently, will continue on-study for an additional 48 weeks after their last study product injection, per the long-term safety and washout PK follow-up (LSFU) schedule.

The sample size for Cohort 2 will be up to 155 adolescents in total. Up to 100 adolescents, who had not previously participated in Cohort 1 (i.e., Cohort 1-naïve), will be enrolled to achieve approximately 70 evaluable. Cohort 2A participants will receive the final recommended oral doses followed by the LA doses of CAB and RPV. Cohort 2B participants will receive the final recommended LA doses of CAB and RPV. Adolescents who participated in Cohort 1 (i.e., Cohort

1 rollovers; up to 55) may continue study participation in Cohort 2, if eligible, in addition to the up to 100 Cohort 2 participants newly enrolled to the study.

At the Week 96/92 visit, Cohort 2A Step 4 and Cohort 2B Step 5 participants continuing to receive injectable CAB LA + RPV LA external to the protocol will exit the study. Section 14.11 of protocol Version 4.0 has more information regarding post-trial access to study products. Participants who discontinue injectable CAB LA + RPV LA at the Week 96/92 visit will not exit the study. These participants will be followed for 48 weeks per the LSFU visit schedule.

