##### No Data in Window

Discontinued study due to Adverse Event or Death:

Any patient who discontinues because of an AE or death before the window should be classified as Discontinued due to AE or Death (as appropriate), regardless of the HIV-RNA result, even if the HIV-RNA is below 50 copies/mL at the time of discontinuation.

However, if a patient has an HIV-RNA value in the time window and also discontinues in the time window, the viral load data should be used to classify the patient's response. This is the Virology First hierarchy:

HIV-RNA below 50 copies/mL at Day 336 and discontinues because of AE or even dies on Day 360 — this person is categorized as having HIV-RNA below 50 copies/mL.

HIV-RNA is 552 copies/mL on Day 336 and the patient discontinues on Day 360, the patient is categorized as having HIV-RNA greater than or equal to 50 copies/mL.

Discontinued for Other Reasons:

Only patients who have achieved virologic suppression can be counted as Discontinued for Other Reasons.

If a patient discontinues the study before the window because of lack of efficacy then the patient should be included in the HIV-RNA greater than or equal to 50 row and not in the Discontinued for Other Reasons row.

If a patient discontinues because of subject withdrew consent and his or her HIV-1 RNA result at the time of discontinuation was equal to or above 50 copies/mL, then he or she should be categorized as HIV-RNA greater than or equal to 50 and NOT as Discontinued for Other Reasons.

If a patient discontinued because of Lost to Follow-Up and the last HIV-RNA result was 49 copies/mL, then the patient can be categorized as Discontinued for Other Reasons.

If patients changed background treatment — not permitted by protocol— they should be considered an efficacy failure and captured in the HIV-RNA greater than or equal to 50 copies/mL row.

On study but missing data in window:

If there are no data during Days 294 to 377, but there is an HIV-RNA below 50 copies/mL on Day 380, this patient should be considered On Study but Missing Data in Window.

If there are no data during Days 294 to 377, but there is an HIV-RNA equal to or above 50 copies/mL on Day 280, this patient also should be classified as On Study but Missing Data in Window.

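### Attachment 2 counts a lack-of-efficacy discontinuation as failure only if the last viral load is at or above the cut-off, contradicting the guidance text reproduced beside it

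*SAP*

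**What the plan says.** SAP Section 3.2 sets the virologic outcomes as HIV-1 RNA at or above 50 and at or above 200 copies/mL, both by the snapshot algorithm. Attachment 2 tabulates the algorithm for 200 only. It is followed by worked examples from FDA guidance, written for 50.

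Condition 5 of the table covers participants caught by none of conditions 1 to 4. For those with no viral load in the window who withdraw, it separates safety from non-safety reasons, and lack of efficacy is in the second group: "Non-safety related reasons (e.g. Lack of efficacy, protocol deviation". That group has three sub-rules:

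- Last on-treatment value below "200 c/mL OR no on-treatment VL available during study": no virologic data, discontinued for other reasons.
- Last on-treatment value at or above "200 c/mL AND withdrawal due to Lack of efficacy": failure, labelled lack of efficacy.
- Last on-treatment value at or above 200 with any other non-safety reason: failure, labelled other reason.

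The examples under No Data in Window address a stop ahead of that period: "because of lack of efficacy then the patient should be included in the HIV-RNA greater than or equal to 50 row". They keep such a patient out of the other-reasons category. No viral load condition is attached. The same text reserves the other-reasons row for patients who have achieved suppression.

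**The concern.** The table and the examples give different answers for the same participant, and a programmer cannot follow both. Under the table, the investigator's judgement that treatment failed has no effect on the response: the last viral load alone decides. A participant taken off the regimen for lack of efficacy whose last value was 120 copies/mL would be reported, at the 200 cut-off, as having no virologic data. A participant with no on-treatment value would go to the same row, although suppression had not been shown on treatment.

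Failure at 50 and at 200 are the only two virologic outcomes in Section 3.2. If failures are few, one misfiled case is visible in the result.

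**Working it through.** The plan states no figure on this point, so the check is of the rules themselves.

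**Step 1: apply both rules.** Take a lack-of-efficacy discontinuation before the window, with no viral load in the window and conditions 1 to 4 not met. The table is written for 200; for 50 I replaced the cut-off and kept the structure. The examples are written for 50; for 200 I carried the same rule over.

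| Cut-off | Last on-treatment value | Attachment 2 table | Reproduced guidance |
|---|---|---|---|
| 50 | none | no data, other reasons | failure |
| 50 | 40 | no data, other reasons | failure |
| 50 | 120 | failure | failure |
| 50 | 300 | failure | failure |
| 200 | none | no data, other reasons | failure |
| 200 | 40 | no data, other reasons | failure |
| 200 | 120 | no data, other reasons | failure |
| 200 | 300 | failure | failure |

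The two rules disagree in five of the eight rows: whenever the last value is below the cut-off or absent.

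**Step 2: what the lack-of-efficacy row does.** The second and third sub-rules both return failure when the last value is at or above the cut-off. Deleting the lack-of-efficacy row and letting the third sub-rule cover all non-safety reasons would leave every response unchanged. Only the reason label would differ.

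**Step 3: where the rule acts.**

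- *All Treated (supplementary).* Section 6.2.2 sends all intercurrent events and missing data through the snapshot. Section 2.1 allows up to 155 participants in Cohort 2.
- *Main set.* Section 6.2.2 handles non-toxicity discontinuation by principal stratum, and Section 4 requires completion through Week 24/20 unless a listed related event occurred. Most lack-of-efficacy stops before that visit are therefore outside the set. Two groups remain: evaluable participants kept in by a related Grade 3 or higher event, and those who stop between Week 24/20 and Week 48/44, if the Week 48/44 analysis uses the Section 4 set as Section 5 says. Section 4 expects approximately 70 in this set.

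**Step 4: size per case.** The shift for one participant is 1/N.

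- N = 155: 1/155 = 0.0065, about 0.6 points.
- N = 70: 1/70 = 0.0143, about 1.4 points.

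For illustration, exact 95% limits for x failures in N are the 0.025 quantile of Beta(x, N − x + 1) and the 0.975 quantile of Beta(x + 1, N − x), with a lower limit of 0 when x = 0. The counts are assumed; the SAP gives none.

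| Failures | N = 70 | N = 155 |
|---|---|---|
| 0 | 0% (0 to 5.1%) | 0% (0 to 2.4%) |
| 1 | 1.4% (0.04 to 7.7%) | 0.6% (0.02 to 3.5%) |
| 2 | 2.9% (0.3 to 9.9%) | 1.3% (0.2 to 4.6%) |

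**The case against.** The best defence is that the conflict is real but rarely matters. Four conditions must coincide: no viral load in the window, none of conditions 1 to 4 met, a recorded reason of lack of efficacy, and a last on-treatment value below the cut-off or absent. The number of such participants may be zero. If restarting other antiretrovirals counts as a non-permitted change in background therapy, condition 1 would already make some of them failures; the SAP does not say whether it does. The planned worst-case analysis in Section 6.2.2 sets missing outcomes to failure and so bounds the effect. All of this stands and limits the size of the point. It does not settle which rule the programmer should follow. The worst case also fails every other participant without data, so it does not show the effect of this rule.

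It can also be said that the examples are for 50 and the table for 200. But Section 3.2 uses the snapshot for both, the table is the only algorithm given, and with 50 put in its place the conflict remains.

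Two stronger inferences are tempting:

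- *The reason for stopping will be unavailable at data lock.* The table takes it from the eCRF Conclusion form, while Section 2.1 says that participants who permanently stop injections early "will continue on-study for an additional 48 weeks after their last study product injection". But the SAP does not say when that form is completed, or that it omits why product was stopped. The safety reasons it lists include liver chemistry stopping criteria, which read as reasons for stopping product. Nor are these participants clearly without a branch: the table defines being on study as product not permanently stopped, and withdrawal reads naturally as the complement. The wording is loose, no more.
- *Multiple imputation will overwrite known failures or deaths*, because values are filled in "for missing study visits prior to implementing the snapshot algorithm". This is a sensitivity analysis only. Nothing says that visits after death or after stopping product count as missing, and the snapshot's on-treatment condition may already exclude them.

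**Conclusion.** The contradiction holds. Condition 5 sends lack-of-efficacy discontinuations with a last value below the cut-off, or with none, to the no-data category. The guidance text in the same attachment sends them to failure, and the table's own lack-of-efficacy row has no effect on any response. Each affected participant moves the failure proportion by about 0.6 points in All Treated at N = 155, or about 1.4 points in the main set at N = 70.

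These sizes assume that enrolment reaches the stated numbers and that participants without virologic data stay in the denominator. The number affected is unknown, so no total effect can be given. A reader might infer that the snapshot rules as a whole always err in the favourable direction. Only this rule does so, by moving a failure to no data; an imputed value could fall either way. Classifying a safety discontinuation with viraemia before the window as no virologic data is also not a defect, since the reproduced guidance prescribes it.

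**What to change.** Reconcile the table with the reproduced guidance. In condition 5, score every lack-of-efficacy discontinuation with no viral load in the window as failure whatever the last on-treatment value, and confine the first sub-rule to the other non-safety reasons. State that this applies at both cut-offs and at Week 24/20 and Week 48/44. If the departure from the guidance is intended, say so and give the reason. Say also how a participant with no on-treatment value fits a row that the guidance reserves for those who achieved suppression.

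As a minor clarification, replace withdrawal in this branch with permanent discontinuation of study product, because Section 2.1 keeps these participants on study in long-term follow-up. Take the reason from the record of product discontinuation.

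The cost is attachment wording and snapshot code, with no new data implied by the classification change. The failure count may rise slightly.

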#### **Examples from FDA guidance (cut-off of 50 copies/mL):**

##### Data in Window

Virologic outcome should be determined by the last available measurement while the patient is on treatment and continued on trial within the time window:

HIV-RNA = 580 copies/mL at Day 336, HIV-RNA below 50 copies/mL on Day 350. This should be categorized as HIV-RNA below 50 copies/mL.

##### No Data in Window

Discontinued study due to Adverse Event or Death:

Any patient who discontinues because of an AE or death before the window should be classified as Discontinued due to AE or Death (as appropriate), regardless of the HIV-RNA result, even if the HIV-RNA is below 50 copies/mL at the time of discontinuation.

However, if a patient has an HIV-RNA value in the time window and also discontinues in the time window, the viral load data should be used to classify the patient's response. This is the Virology First hierarchy:

HIV-RNA below 50 copies/mL at Day 336 and discontinues because of AE or even dies on Day 360 — this person is categorized as having HIV-RNA below 50 copies/mL.

HIV-RNA is 552 copies/mL on Day 336 and the patient discontinues on Day 360, the patient is categorized as having HIV-RNA greater than or equal to 50 copies/mL.

Discontinued for Other Reasons:

Only patients who have achieved virologic suppression can be counted as Discontinued for Other Reasons.

If a patient discontinues the study before the window because of lack of efficacy then the patient should be included in the HIV-RNA greater than or equal to 50 row and not in the Discontinued for Other Reasons row.

If a patient discontinues because of subject withdrew consent and his or her HIV-1 RNA result at the time of discontinuation was equal to or above 50 copies/mL, then he or she should be categorized as HIV-RNA greater than or equal to 50 and NOT as Discontinued for Other Reasons.

If a patient discontinued because of Lost to Follow-Up and the last HIV-RNA result was 49 copies/mL, then the patient can be categorized as Discontinued for Other Reasons.

If patients changed background treatment — not permitted by protocol— they should be considered an efficacy failure and captured in the HIV-RNA greater than or equal to 50 copies/mL row.

On study but missing data in window:

If there are no data during Days 294 to 377, but there is an HIV-RNA below 50 copies/mL on Day 380, this patient should be considered On Study but Missing Data in Window.

If there are no data during Days 294 to 377, but there is an HIV-RNA equal to or above 50 copies/mL on Day 280, this patient also should be classified as On Study but Missing Data in Window.
